16.4.3 Sensitivity Analyses of the Primary Endpoint

Five sensitivity analyses of the primary endpoint will be conducted using each of the following modifications to the definition of PFS:

- If the disease recurrence/progression assessment involves more than one date, the latest date will be used as the event date.
- If disease recurrence or death occurs right after missing data for a scheduled radiographic disease assessment (including missing the assessment or assessment results in an unevaluable status for overall response per RECIST 1.1), the patient will be censored at the date of the last radiographic disease assessment.
- If a patient receives non-protocol treatment for Ewing's Sarcoma, the patient will be treated as having progression at the date of the last radiographic disease assessment.
- Patients missing baseline disease assessment will be treating as had having progression at the date of randomization.
- For equivocal findings of recurrence (e.g., very small and uncertain new lesions; cystic changes or necrosis in existing lesions) for whom treatment continues until the next scheduled assessment, and if recurrence is confirmed at the next scheduled assessment, the date of recurrence should be the date when recurrence was confirmed.

16.4.4 Sensitivity Analysis of Overall Survival

A sensitivity analysis of OS will be conducted in which subjects who are crossed over to Vigil therapy will be censored at the time of crossover.

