The NCCN guidelines do not provide standard of care recommendations for second-line treatment and only 9-13% of patients achieve a second disease free remission (Bacci, Ferrari et al. 2003, Barker, Pendergrass et al. 2005, Rasper, Jabar et al. 2014). In one large retrospective analysis of 714 patients in first relapse, the 1-year OS was 43%, 5-year OS was 13%, and 10-year OS was 9% (Stahl, Ranft et al. 2011).

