1.3 Salvage chemotherapy in Ewing's sarcoma

Regimens such as topotecan/cyclophosphamide, irinotecan/temozolomide, or docetaxel/gemcitabine have been utilized in second line or later treatment and may prolong life for those who respond (Merchant, Kushner et al. 1999, Saylors, Stine et al. 2001, Wagner, Crews et al. 2004, Wagner, McAllister et al. 2007, Navid, Billups et al. 2008, Navid, Willert et al. 2008, Casey, Wexler et al. 2009, Mora, Cruz et al. 2009, Wagner 2010, Wagner, Perentesis et al. 2010, McGregor, Stewart et al. 2011, Rapkin, Qayed et al. 2012, Raciborska, Bilska et al. 2013, Wagner, Turpin et al. 2013). Although results of progression free survival (PFS) and OS do not significantly vary between dose regimens (Yildiz, Sen et al. 2014), PFS in patients treated with second-line irinotecan/temozolomide, the most commonly used regimen, varies between 3 and 8 months with most commonly reported PFS of 6 months (Casey, Wexler et al. 2009, Raciborska, Bilska et al. 2013, Palmerini, Jones et al. 2016).

Clinical studies have demonstrated the combination of irinotecan and temozolomide to have synergy and significant antitumor activity. Casey et al. showed that the combination of temozolomide and irinotecan is well-tolerated and an active regimen for recurrent or refractory Ewing's sarcoma patients (first relapse) with an overall response of 63% and median TTP of 8.3 months (Casey, Wexler et al. 2009).

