10.0 CROSS-OVER

Subjects randomized to Group B may cross-over to Group A after discussion with, and approval from the Gradalis medical monitor or authorized designee.

Within 6 weeks of second relapse or progression and if alternative therapy has not been given since EOT, subjects randomized to Group B, will be allowed to cross-over to receive single agent Vigil every 21 days following End of Treatment assessment. Subjects who cross-over may receive up to 12 doses of Vigil depending upon the quantity of Vigil manufactured. After the Group B EOT assessment, the subject will start "cross-over" from Assessments During Treatment onward. Vigil and all assessments will occur on Day 1 of each cycle.

Cross-over must occur within 2 years of End of Treatment assessments of Group B enrollment. Subjects who progress \geq 8 weeks post EOT assessment must re-screen and if they qualify will start "cross-over" from Assessments During Treatment onward. Eligibility criteria for cross-over subjects are listed below.

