10.1 Inclusion Criteria for Cross-Over

Subjects will be eligible for cross-over, if they meet all of the following criteria:

- 1. Evidence of radiologic disease progression by RECIST 1.1 after enrollment into Group B.
- 2. Successful manufacturing of at least 4 vials of Vigil.
- 3. Karnofsky performance status (KPS) / Lansky performance status (LS) ≥70%.
- 4. Normal organ and marrow function as defined below:

Absolute granulocyte count	≥1,000/mm³	
Absolute lymphocyte count	≥400/mm³	
Platelets	≥75,000/mm³	
Total bilirubin	≤ institutional upper limit of normal	
AST(SGOT)/ALT(SGPT)	≤2x institutional upper limit of normal	
Creatinine	<1.5 mg/dL	

*documented Gilbert's syndrome may be considered after medical monitor review

- 5. Subject has recovered to CTCAE Grade 1 (except for parameters noted in Item 4, above) or better from all adverse events associated with prior therapy or surgery. Preexisting motor, sensory neurologic pathology or symptoms, or dermatologic toxicities must be recovered to CTCAE Grade 2 or better.
- 6. If female of childbearing potential, has a negative urine or serum pregnancy test. If the urine test is positive or cannot be confirmed as negative, a negative serum test will be required for study entry.
- 7. Ability to understand and the willingness to sign a written informed protocol specific consent or a parental/guardian informed consent and pediatric assent when appropriate.

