10.2 Exclusion Criteria for Cross-Over

In addition to the Procurement and Study Enrollment exclusion criteria, Subjects will NOT be eligible for cross-over if meeting any of the following criteria:

- 1. With the exception of irinotecan and temozolomide while on study, any anti-neoplastic therapy between tissue procurement for Vigil manufacture and start of study therapy.
- 2. Live vaccine used for the prevention of infectious disease administered < 30 days prior to the start of study therapy.

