16.0 STATISTICAL CONSIDERATIONS

16.1 Sample Size Justification

This is an open label randomized controlled Phase III clinical trial. Information concerning the predicted survival of the control group is limited, based on rarity of disease and few published reports. However expert advisors in the EWS field estimate a conservative one-year survival rate of 25% in the chemotherapy control group. The one-year survival rate of 60% in the Vigil treated group is estimated from EWS patients treated on the Vigil phase 1 protocol. These estimates correspond to a hazard ratio (HR) of 0.383 favoring Vigil over control.

Assuming 1:1 randomization and the use of a two-sided log rank test at the alpha=0.0476 level of significance, 67 events will provide 90% power to detect an PFS HR of 0.45. Assuming a Group B (control group) median PFS of 6 months, a one-year accrual period, and a six-month follow-up period after randomization of the last subject, it is estimated that the total sample size (number of subjects) required to achieve 67 events is 114 (57 patients in each arm).

An unblinded interim analysis will be conducted by an independent data monitoring committee (IDMC) when 40 PFS events have occurred. Based on the results of this interim analysis, the planned sample size may be increased to 120 events. If the sample size is increased to 120 events, then the study will have approximately 90% power to detect a true HR of 0.55. Note that if the sample size is increased to 120 events, then the accrual period will be extended to 24 months, with a 6-month follow-up period after randomization of the last patient. Under these assumptions, it is estimated that approximately 164 patients will need to be randomized in order to achieve 120 events. Section 16.6 provides further details.

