16.3 Analysis Populations

The intent-to-treat (ITT) population will include all randomized subjects. All efficacy analyses will be completed in the ITT population.

The Safety population will include all patients who receive study treatment and patients will be analyzed according to actual treatment received. All safety analyses will be completed in the Safety population.

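### Does the overall survival sensitivity analysis that censors at cross-over need to be changed?

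*Protocol*

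**What the plan says.** Protocol 16.4.4 and SAP 8.1.4 give the same single sentence: "subjects who are crossed over to Vigil therapy will be censored at the time of crossover". Neither adds an assumption, a target quantity, a test or an alpha level.

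The route to cross-over is in Protocol section 10:
- Timing and prior therapy (10.0): "Within 6 weeks of second relapse or progression and if alternative therapy has not been given since EOT". Approval by the sponsor's medical monitor is also needed.
- Progression (10.1): "Evidence of radiologic disease progression by RECIST 1.1 after enrollment into Group B".
- Fitness (10.1): Karnofsky or Lansky score of at least 70%, laboratory limits and recovery from toxicity. The score limit is looser than the 80% required at enrolment (6.4).
- Exclusion (10.2): "With the exception of irinotecan and temozolomide while on study, any anti-neoplastic therapy between tissue procurement for Vigil manufacture and start of study therapy".

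On the main analysis, Protocol 16.3 says "All efficacy analyses will be completed in the ITT population". Section 16.4.2 tests OS by a two-sided log-rank test, after PFS and before response rate in a fixed sequence. The cross-over analysis is not in that sequence.

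**The concern.** Censoring is harmless only if those censored have the same later risk of death as those who stay under observation. Here the rule that permits the switch breaks that condition, in one arm only. Two effects pull in opposite directions:

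- Patients leave the Group B risk set just after progression, when their death risk has risen. What remains is richer in patients who have not progressed, so control looks better and the hazard ratio moves against Vigil.
- Among progressors, the fitter ones leave. The less fit remain, so control looks worse and the hazard ratio moves in favour of Vigil.

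At stake is how OS is read in an open-label trial that offers the product to its control arm. Agreement between this analysis and the intention-to-treat result could be taken as robustness, and disagreement as absence of benefit. Neither inference is safe.

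**Working it through.** **1. Design figures.** The sensitivity analysis has no figure of its own, so the PFS design behind it was checked first.

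Events: 4(z₁ + z₂)² / (ln HR)² with z₁ = 1.981 (two-sided 0.0476), z₂ = 1.282 (90% power) and HR 0.45. This is 4 × 3.263² / 0.7985² = 66.8, so 67 as planned.

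Subjects: with hazard λ, 12 months' accrual and 6 months' follow-up, P(event) = 1 − (e^(−6λ) − e^(−18λ)) / (12λ).
- Control: λ = ln 2 / 6 = 0.1155, giving 0.729.
- Vigil: 0.45λ = 0.0520, giving 0.455.
- Mean 0.592, and 67 / 0.592 = 113.1, against 114 planned.

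**2. Which control survival to use.** Protocol 16.1 reports that "expert advisors in the EWS field estimate a conservative one-year survival rate of 25% in the chemotherapy control group". With an exponential PFS median of 6 months, one-year PFS is 2^(−12/6) = 25%, which leaves no room for survival after progression. The check therefore uses the background figure in Protocol 1.2, "714 patients in first relapse, the 1-year OS was 43" per cent. That is an assumption, not a design input.

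**3. Model.** Control PFS is exponential with hazard λ. A share q of PFS events are deaths, which cannot cross over. A share p of progressors are due to switch 3 weeks after progression if still alive. Death hazard after progression is μ for non-switchers and kμ for switchers. The value of μ is solved from

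e^(−12λ) + (1 − q) Σ pⱼ λ (e^(−12μⱼ) − e^(−12λ)) / (λ − μⱼ) = 0.43,

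summing over switchers and non-switchers. Where Vigil works (PFS HR 0.45), it is assumed to cut hazard after the switch by 40%. The documents do not give p, k, q, the switch time or the 40%.

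**4. Results.** Cox hazard ratios for OS at 12 + 6 months. Ranges are the spread over independent simulation runs.

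*No Vigil effect (the intention-to-treat HR stays within 0.01 of 1.00)*

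| Crossing p, relative hazard k | q = 0 | q = 5% | q = 20% |
|---|---|---|---|
| 50%, 0.5 | 1.32–1.33 | 1.27–1.28 | 1.17–1.18 |
| 30%, 0.2 | 1.02 | about 1.00 | 0.98 |
| 70%, 1.0 | 1.86–1.88 | 1.74 | 1.45 |

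*PFS HR 0.45*

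| Setting | No cross-over | Intention to treat | Censored |
|---|---|---|---|
| 50%, k = 0.5, q = 0 | 0.47–0.48 | 0.55–0.56 | 0.63–0.65 |
| Same, q = 5% | 0.48 | 0.54–0.55 | 0.61–0.62 |
| Same, q = 20% | 0.49 | 0.54–0.55 | 0.56–0.57 |
| 30%, k = 0.2–0.35 | 0.48–0.49 | 0.51–0.53 | 0.48–0.52 |
| About 70%, k = 0.5, q = 0 | 0.48 | 0.58 | 0.83–0.86 |

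**5. Direction.** A separate grid of 96 settings at each OS level varied the fit share, fitness contrast, uptake, share of deaths and PFS HR (0.45 or 1). The error was against Vigil in 96 of 96 at one-year OS of 30%, 84 of 96 at 43% and 68 of 96 at 55%. Protocol 1.3 says PFS on this regimen "varies between 3 and 8 months with most commonly reported PFS of 6 months". At a 4-month median and 43% OS, with q = 0, the null censored HR spans 0.85–1.66. The direction is likely but not certain.

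**6. Scale.** The larger central shift, from 0.55 to 0.65, is ln(0.65 / 0.55) = 0.17 on the log scale. The sampling SD of the intention-to-treat log HR at 114 patients is 0.30–0.31, so the shift is about half of one SD.

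**7. What an adjusted analysis would offer.** A two-stage analysis of Group B progressors, with a landmark at 6 weeks and about half crossing, leaves about 15 switchers (8 deaths) and 6 eligible non-switchers (4 deaths) at 114 patients. The SD of its log HR is 0.33, so the 95% limits are a factor of e^(1.96 × 0.33) = 1.9 either way. It cannot be fitted in 2–3% of simulated trials. If unrecorded fitness drives switching, its HR under no effect is 0.83–0.97 over the 114- and 164-patient designs, which leans towards Vigil.

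**The case for a change.** The strongest case for a change is that this is the only planned look at cross-over, and its assumption fails by the protocol's own rules. In the central setting it lands further from the no-cross-over value than the intention-to-treat analysis it is meant to check (0.63–0.65 and 0.55–0.56, against 0.47–0.48). One sentence in each document would warn the reader at almost no cost, and a warning added after unblinding might look chosen to suit the result.

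The facts in this stand. The conclusion does not follow. The sentence would alter no estimate, test or decision, and it would correct no statement, because the plan describes the analysis only as a sensitivity analysis. That censoring at a switch assumes independence is inherent in the method, and it can be stated at reporting, with the number and timing of cross-overs, without choosing among analyses after seeing data. A flat statement that the analysis misses OS without cross-over would also be too strong: with 30% crossing and strong selection it comes as close as intention to treat, or closer.

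A related mismatch is clerical. Footnote 6 of the SAP schedule lists only survival status after progression, while the Protocol (section 9.0, Long Term Follow Up, and Appendix B) also lists post-study therapies. The Protocol collects them, and SAP 1.0 refers the reader to the protocol and case report forms for data collection.

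**Conclusion.** The censoring is informative, and the analysis does not in general estimate OS without cross-over. With a 6-month PFS median, one-year OS of 43%, half of progressors due to cross and half hazard in switchers, a true HR of 1.00 would appear as about 1.33 with no deaths among PFS events and about 1.18 with 20% deaths. With 30% crossing and strong selection it would appear as about 0.98 to 1.03. All of these inputs except the PFS median are assumed rather than design values.

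No change to the plan follows. The confirmatory OS test is unaffected and no claim rests on the censored result. Its error usually runs against Vigil, so a false claim of benefit is not the likely harm. A label would be harmless but would change nothing. The adjusted alternative trades a visible bias for a sparse, fragile estimate that may lean towards the product. Keeping the simple analysis as a supportive reading beside intention to treat is a fair choice, provided it is read with the limits above in mind.

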16.4.5 Subgroup Analyses of the Primary (PFS) and Key Secondary Endpoints (OS, ORR)

Subgroup analyses will be conducted in the following subsets of the ITT population:

- Race / ethnicity
- Study site / region
- Age group (<15 years (low), ≥15 years (high))
- Gender
- Number of doses received (≤median number of doses administered, >median number of doses administered)
- Number of lines of prior treatments including chemotherapy and radiation
- At time of diagnosis: localized vs. metastatic disease
- At time of diagnosis: skeletal vs. extraskeletal
- At time of diagnosis: tumor volume/burden (<100ml or 8cm vs >100ml or 8cm)
- Response to frontline therapy (CR vs. PR vs. SD vs. progressive disease)
- Time to first recurrence: <2 years, > 2 years

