7.0 WITHDRAWAL

7.1 Discontinuation from Study Treatment

Treatment will be continued until progressive disease by RECIST 1.1. However, insofar as some patients in our early vaccine trials had increased survival despite initial, short-term volume increase. There is accumulating evidence that some subjects treated with immune system stimulating agents may appear to demonstrate progression of disease by conventional response criteria before demonstrating clinical objective responses and/or stable disease and ultimately survival benefit. It may be that enhanced inflammation within tumors initially leads to an increase in tumor size or newly visible small lesions. Over time, both the malignant and inflammatory portions of the mass may then decrease leading to overt signs of clinical improvement.

Therefore, selected subjects may be allowed to continue study therapy after investigatorassessed RECIST 1.1 progression and with agreement by the Gradalis medical monitor if the subject is determined to be deriving clinical benefit, tolerating study drug and meeting the following criteria:

- 1. Absence of symptoms and signs indicating clinically significant PD indicating disease progression.
- 2. No decline in ECOG performance status.
- 3. Absence of rapid progression of disease or of progressive tumor at critical anatomical sites (e.g., cord compression) requiring urgent alternative medical intervention.

If subsequent imaging shows an objective response or stable disease relative to baseline, treatment with study agents will continue. If subsequent imaging again shows PD, patients will be discontinued from study therapy.

Subjects will discontinue **study treatment** if any of the following occur:

- 1. Disease progression by RECIST 1.1 criteria.
- 2. The patient experiences unacceptable (≥Grade 3) toxicity felt to be related to treatment with the Vigil immunotherapy that persists for >3 weeks. Subjects would be discontinued from both Vigil and chemotherapy.
- 3. The subject experiences unacceptable (≥Grade 3) toxicity felt to be related to treatment with irinotecan/temozolomide that persists for >3 weeks. Vigil therapy may be continued in monotherapy.
- 4. Persisting Grade 3 or 4 toxicity unrelated to treatment, defined as failing to normalize within 3 weeks.
- 5. Any Grade \geq 3 allergic reactions related to Vigil.
- 6. Grade 2 autoimmune reactions unless there is evidence of clinical benefit.

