7.2 Treatment Delay

- Treatment may be delayed no more than 3 weeks to allow recovery from toxicity.
- If ≥ one 2-week delay due to disease or infection occurs, subject status must be reviewed by sponsor.
- If subjects miss doses, the doses will be made up the following week and continue on a revised every 3-week schedule thereafter.

If Vigil administration is delayed, then irinotecan and temozolomide should concurrently be delayed.

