8.4.1 Schedule, Dose and Administration

	Drug	Dose	Schedule	
	Temozolomide 100 mg/m ² daily, oral		Days 1 – 5, every 21 days	
Group A	Irinotecan 50 mg/m ² daily, oral		Days 1 – 5, every 21 days	
	Vigil	1.0 x 10 ⁶ cells/injection, intradermal	Day 15, every 21 days	

Cross-Over	Drug	Dose	Schedule
Subjects	Vigil	1.0 x 10 ⁶ cells/injection, intradermal	every 21 days

Subjects will receive Vigil at 1.0×10^6 cells via intradermal injection **every 3 weeks for a minimum of 4 administrations to** a maximum of 12 administrations depending on quantity of Vigil manufactured from surgical specimens and so long as the patient is clinically stable and without disease progression.

The sites of injection for Vigil will be rotated between the right and left upper arms. If the ipsilateral axillary lymph nodes were radiated or surgically removed during prior therapy, alternative sites may be used.

	Drug	Dose	Schedule
Group B Temozolomide		100 mg/m² daily, oral	Days 1 – 5, every 21 days
	Irinotecan	50 mg/m² daily, oral	Days 1 – 5, every 21 days

Please contact the sponsor with any dose adjustment considerations.

Irinotecan Preparation

Order the injectable formulation of irinotecan from central supplier, Clinigen. Draw up 1 cycle of (five doses) into provided oral syringes and dispense to the subject with instructions to refrigerate until administration. Irinotecan may be mixed with cranberry-grape juice before administration to mask the bitter flavor and administered once daily on Days 1 through 5 of each 3-week cycle.

Temozolomide Preparation

Temozolomide capsules for 1 cycle will be obtained by the patient with administration instructions. Temozolomide may be opened and mixed in apple sauce or juice if unable to swallow whole capsules. Temozolomide is administered on Days 1 through 5 of each 3-week course and given at least 1 hour before irinotecan.

Subjects should be instructed to complete a dosing diary for the administration of oral irinotecan and oral temozolomide.

Premedications and post medications

Vigil: EMLA® may be utilized at the injection site prior to Vigil administration. Analgesics may be employed as necessary. As noted above, systemic steroids or other immunosuppressants should be avoided due to immune inhibition activity.

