Temozolomide / irinotecan: Per package inserts and institutional standards. A home supply of anti-emetic (e.g. ondansetron) is highly recommended to take before temozolomide and as needed. Also, a patient supply of an anti-diarrheal medication (e.g. loperamide) should be available after irinotecan for use as needed.

The patient should be educated with a study calendar indicating days to get chemotherapy and/or Vigil as well as supportive care medications and when Vigil is given.

Vigil Immunotherapy Transfer

All manufactured Vigil will be stored in the vapor phase of liquid nitrogen until ready for use. The site will contact Gradalis, Inc. when the study agent is needed for subject administration.

Gradalis will complete a Drug Transfer and Administration Form to release the subject vaccine. The clinic will sign off on the form upon receipt of the administration.

Please reference the Study Reference Manual for preparation and handling information.

Dose Modification for Vigil Toxicity

If > Grade 2 toxicity by NCI Common Toxicity Criteria (excluding Grade 3 injection site reactions) develops related to study treatment the Vigil dose will be reduced by 50% and continued.

Dose Modifications for temozolomide and irinotecan

Dose modifications for temozolomide, and irinotecan may be necessary for subject safety and should be carried out in accordance with the Investigator's standard of practice, the package inserts, and institutional standards. Please contact the sponsor regarding any dose modifications.

If irinotecan + temozolomide is administered beyond 12 cycles, it will be administered off study and no longer provided by Gradalis.

If irinotecan + temozolomide is discontinued, Vigil may be administered every 3 weeks until all manufactured product is exhausted or when disease progression is noted.

Study Regimen Delay

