- 8. Serum chemistries (creatinine, glucose, total protein, blood urea nitrogen (BUN), total carbon dioxide (CO2), albumin, total bilirubin, alkaline phosphatase, and aspartate transaminase (AST) and/or alanine transaminase (ALT)) and electrolytes (total calcium, chloride, potassium, sodium) must be performed.
- 9. Blood collection for immune function analysis (ELISPOT).
- 10. Plasma collection for immune function analysis (ctDNA).
- 11. Pregnancy test for those of childbearing potential.
- 12. Submission to Gradalis, Inc. of preferably 20 unstained tumor slides or tissue block for correlative immunohistochemistry assay. These slides should correlate with tumor procured for vaccine manufacture.

Assessments During Treatment

The following evaluations will be performed on Day 1 of each cycle (1 Cycle = 21 days \pm 3 days) (unless otherwise specified):

- 1. *A physical examination, including vital signs and body weight.
- 2. *A toxicity assessment (CTCAE v 5).
- 3. *Assessment of concomitant medications.
- 4. Radiological assessment of disease status with CT chest /abd/pelvis (MRI abd/pelvis may be substituted for CT abd/pelvis) every 6 weeks ± 7 days from Cycle 1 regardless of treatment arm assignment or treatment delay. The methods used for prestudy assessments (e.g., CT or MRI) should be used throughout the study. If possible, the same equipment should be used each time.
- 5. *A CBC with differential and platelet count.
- 6. *Serum chemistries (creatinine, glucose, total protein, blood urea nitrogen (BUN), total carbon dioxide (CO2), albumin, total bilirubin, alkaline phosphatase, and aspartate transaminase (AST) and/or alanine transaminase (ALT)) and electrolytes (total calcium, chloride, potassium, sodium).
- 7. Blood collection for immune function analysis (ELISPOT) on Day 1 (prior to chemotherapy administration) at Cycles 2, 4, and 6.
- 8. Plasma collection for immune function analysis (ctDNA) on Day 1 prior to chemotherapy administration at Cycles 2, 3, 4 and 6.
- 9. *Assessment of Karnofsky Performance Status or LS.
- 10. Group A and B participants: oral temozolomide 100 mg/m² daily (Days 1 5, total dose 500 mg/m²/cycle)
- 11. Group A and B participants: oral irinotecan 50 mg/m² daily (Days 1 5, total dose 250mg/m²/cycle)
- 12. Group A participants: Vigil 1.0 x 10⁶ cells/injection, intradermally on Day 15.
- 13. Cross-over Subjects: Vigil 1.0 x 10⁶ cells/injection, intradermally every 21 days

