13.1 Exposure to Study Drug

Study treatment dosing compliance will be summarized with descriptive statistics by treatment group. All exposure and compliance data will be provided in data listings.

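### The doses-received subgroup splits PFS, OS and ORR on a post-randomisation count that depends partly on staying progression-free, and does not say where Group B belongs

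*Protocol*

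**What the plan says.** Protocol 16.4.5 and SAP 8.1.5 carry the same list of 11 subgroup lines for the ITT population, covering PFS, OS and ORR. One line is "Number of doses received (≤median number of doses administered, >median number of doses administered". ITT is all randomised subjects (Protocol 16.3, SAP 8.0), so Group B has to fall somewhere. Neither document names the drug, says whose median applies, places Group B, or gives a landmark or time-dependent method.

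Protocol 8.4.1 caps Vigil at 12 injections and sets two further limits on the count: "depending on quantity of Vigil manufactured from surgical specimens and so long as the patient is clinically stable and without disease progression". Section 7.1 stops treatment at RECIST progression, but "selected subjects may be allowed to continue study therapy" past it. Group B receives Vigil only on cross-over after progression: "Subjects who cross-over may receive up to 12 doses of Vigil depending upon the quantity of Vigil manufactured" (section 10.0). Both arms also receive chemotherapy, with a ceiling on study: "If irinotecan + temozolomide is administered beyond 12 cycles, it will be administered off study". At least 4 vials must have been made before a patient is randomised (Protocol 5.0 and 6.4). SAP 13.1 separately provides that "Study treatment dosing compliance will be summarized with descriptive statistics by treatment group".

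**The concern.** This is the only one of the 11 lines defined by treatment received after randomisation. A patient who progresses early cannot accumulate many doses, so for some patients the subgroup variable is a consequence of the endpoint. The comparison within a subset is then no longer a randomised one.

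On the Vigil reading the display would tend to place early progressors under low dose and later ones under high dose. In an open-label Phase III trial, a pre-specified table of that kind could be read as a dose-response even if Vigil did nothing. The table also cannot be programmed without guessing where Group B goes and whether cross-over doses count. If they do, Group B is classified by treatment given after its PFS event.

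**Working it through.** **Design figures (Protocol 16.1), reproduced first.** Schoenfeld events = 4(z₁₋α/₂ + z₁₋β)² / (ln HR)² = 4(1.981 + 1.282)² / (ln 0.45)² = 42.6 / 0.638 = 66.8, so 67, as stated. With exponential PFS, accrual A = 12 and follow-up F = 6 months, P(event) = 1 − [e^(−λF) − e^(−λ(A+F))] / (λA). This is 0.729 for the 6-month control median and 0.455 at HR 0.45. N = 67 / [(0.729 + 0.455)/2] ≈ 113, against 114 stated. The same model is used below.

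**Hand check of the mechanism.** Take Cycle 1 Day 1 as randomisation. Vigil dose k falls on Day 15 + 21(k − 1), and scans are "every 6 weeks ± 7 days from Cycle 1 regardless of treatment arm assignment or treatment delay". If the Group A median is 5 doses, the upper subset needs a sixth dose, on Day 120. Nobody with progression detected by the scan at 84 days can be in it. With a 6-month (182.6-day) median and no treatment effect, 1 − 0.5^(84/182.6) = 27% of an unselected arm has progressed by then. If the median is 6, the seventh dose is on Day 141, the last earlier scan is at 126 days, and the figure is 1 − 0.5^(126/182.6) = 38%. The upper subset excludes these patients by construction, and Group A's share of them goes to the lower subset.

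**Simulation.** Dosing runs until detected progression, data cut-off or the last vial. Events are dated to the next 6-weekly scan, and hazard ratios come from a Cox model. Vial supply per patient is assumed, because the documents do not give it. Low and high are relative to the Group A median, with Group B at 0 doses.

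| PFS quantity | 4–5 vials | 4–8 | 4–12 |
|---|---|---|---|
| Dosing ended before vials ran out, no effect | 21% | 29% | 41% |
| The same, true HR 0.45 | 10% | 15% | 23% |
| Group A median doses, no effect | 4 | 5 | 6 |
| Lower subset: low-dose Group A vs all Group B, no effect | 1.30 | 1.44 | 1.64 |
| Illustration: high vs low dose within Group A, no effect | 0.50 | 0.45 | 0.30 |

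The plan specifies "Treatment may be delayed no more than 3 weeks to allow recovery from toxicity". Adding delays (assumed 15% of doses, 1–3 weeks) and toxicity stops (assumed 10% of patients) gives a lower-subset HR of 1.29 / 1.45 / 1.85. Also adding two further doses in an assumed 25% of progressors gives 1.27 / 1.42 / 1.55. In trials of 57 per arm with delays and stops, the median and 5th–95th percentiles are 1.30 (0.86–1.96), 1.50 (0.96–2.46) and 1.70 (1.10–2.82). With a true HR of 0.45, the lower subset shows 0.57–0.68.

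**Other readings.** If the median is taken over the whole ITT population with Group B at 0, the lower subset holds only 0 to about 3 of the 57 Group A patients. If chemotherapy cycles were meant, both arms have values and null hazard ratios stay near 1, but a true 0.45 appears as roughly 0.6–0.7 in the low-cycle subset.

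**Check of the replacement.** Splitting on doses manufactured gives 0.99–1.02 when the truth is 1.0, and 0.44–0.46 when it is 0.45.

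**The case against.** The strongest case on the other side has four parts.

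- **Only a subgroup line.** It is one of 11, with no alpha attached. That stands. A reader might infer that the primary result or the error rate is compromised, but the log-rank test, the fixed sequence in 16.4.2 and the interim rules in 16.6 do not use this variable.
- **Supply dominates.** A reader might infer that the dose count is essentially PFS under another name. It is not. In the model, vial supply sets the count for 79% / 71% / 59% of Group A with no effect, and for more at HR 0.45. The progression-driven part is still enough to move the lower-subset hazard ratio.
- **The dose-response contrasts are not in the plan.** Also true. On the Vigil reading the upper subset has no PFS controls and yields no hazard ratio. The high-versus-low figures show what a reader could construct from the table. The one hazard ratio the plan could produce is the lower-subset one, and at 57 per arm its 5th–95th percentile range includes 1 in two of the three supply scenarios.
- **The chemotherapy reading is weak.** The documents mostly attach the word doses, with its limit of 12, to Vigil. A reader might also infer that on the cycle reading the upper subset would often be empty at the 12-cycle ceiling. That happens in about 45% of simulated trials at HR 0.45 with no delays or toxicity stops, but in only 5–6% with delays and about 1% or fewer with both.

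**Conclusion.** The line should be changed. As written, it conditions on a post-randomisation count that is partly determined by the endpoint, and it is not defined well enough to programme. On the likely (Vigil) reading, with no true effect, the lower-subset PFS hazard ratio is about 1.3 / 1.4 / 1.65 for assumed supplies of 4–5 / 4–8 / 4–12 vials. A reader-made contrast within Group A would be about 0.5 / 0.45 / 0.3. The direction follows from the dosing rule. The size rests on assumed vial supply, exponential PFS and the plan's 6-month control median. On the cycle reading there is no false effect under the null, only distortion of a real one. For OS and ORR only the direction is claimed: patients must live or stay progression-free long enough to collect many doses. Confirmatory inference is untouched.

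**What to change.** In Protocol 16.4.5 and SAP 8.1.5, replace the line with: *Number of Vigil doses manufactured before randomization (≤median vs >median of all randomized subjects; not presented if either subset has fewer than 10 subjects in either arm)*. This count is fixed before randomisation in both arms. The alternative is to delete the line and keep doses received as descriptive exposure under SAP 13.1.

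If an exposure analysis is wanted, make it exploratory, in Group A only, with no comparison to Group B:

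- **PFS:** cumulative doses as a time-dependent covariate; or, among subjects progression-free at a landmark fixed in the SAP, the count of doses received up to that landmark, with time measured from it. With no true effect these give hazard ratios per dose of 0.994–1.003 and 0.990–1.009 (landmark Day 168).
- **OS:** the landmark version only, and only among subjects progression-free at the landmark. Being merely alive is not enough, because dosing stops at progression. With no Vigil effect and an assumed post-progression median survival of 4–12 months, conditioning on being alive at Day 168 gives about 0.71–0.75 / 0.83–0.85 / 0.83–0.86 per dose. Requiring progression-free status gives 1.00–1.03. The time-dependent version should not be offered for OS, for the same reason.
- **ORR:** not presented by doses received.

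The landmark must be later than Day 84, when every patient on schedule has had exactly 4 doses (Days 15, 36, 57 and 78).

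The cost is one line per document, plus the optional passage. The manufactured count may need adding to the analysis dataset. It reflects tissue yield rather than exposure. With the 10-per-arm rule it would go unshown in about 46% of trials if supply is 4–5 vials, always if every patient has 12, and in 0.1% or fewer with 4–8 or 4–12.
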